6.1.4 Trametinib Dose Modification for Diarrhea

Episodes of diarrhea have occurred in patients receiving trametinib (Investigator's Brochure, 2012a). Other frequent causes of diarrhea including concomitant medications (e.g., stool softeners, laxatives, antacids, etc.), infections by *C. difficile* or other pathogens, or partial bowel obstruction should be clinically excluded.

Guidelines regarding management and dose modification for diarrhea considered related to trametinib are provided in the table below.

Management and Trametinib Dose Modification Guidelines for Diarrhea		
CTCAE Grade	Adverse Event Management	Action and Dose Modification
Uncomplicated Diarrhea,¹ Grade 1 or 2	
Diet: Stop all lactose containing products; eat small meals, BRAT-diet (banana, rice, apples, toast) recommended.Hydration: 8-10 large glasses of clear liquids per day (e.g., Gatorade or broth).Loperamide³: Initially 4 mg, followed by 2 mg every 4 hours or after every unformed stool; maximum 16 mg/day. Continue until diarrhea-free for 12 hours.Diarrhea >24 hours: Loperamide 2 mg every 2 hours; maximum 16 mg/day. Consider adding oral antibiotics.Diarrhea >48 hours: Loperamide 2 mg every 2 hours; maximum 16 mg/day. Add budesonide or other second-line therapies (otreotide, or tincture of opium) and oral antibiotics.	
Continue trametinib.If diarrhea is grade 2 for > 48 h, interrupt trametinib until diarrhea resolves to grade ≤ 1.Restart trametinib at the same dose levelIf treatment delay is >4 weeks, discontinue trametinib.

Management and Trametinib Dose Modification Guidelines for Diarrhea		
CTCAE Grade	Adverse Event Management	Action and Dose Modification
Uncomplicated Diarrhea,¹ Grade 3 or 4 Any Complicated Diarrhea²	
 Clinical evaluation mandatory. Loperamide³: Initially 4 mg, followed by 2 mg every 4 hours or after every unformed stool; maximum 16 mg/day. Continue until diarrhea-free for 12 hours. Oral antibiotics and second-line therapies if clinically indicated. Hydration: Intravenous fluids if clinically indicated. Antibiotics (oral or intravenous) if clinically indicated. Intervention should be continued until the subject is diarrhea-free for \geq24 hours. Intervention may require hospitalization for subjects at risk of life-threatening complications. 	
 Interrupt trametinib until diarrhea resolves to \leq grade 1. Restart with trametinib reduced by one dose level.⁴ If 3 dose reductions of study treatment are clinically indicated, permanently discontinue trametinib. If treatment delay is >4 weeks, discontinue trametinib.

1. **Uncomplicated diarrhea** defined by the absence of symptoms such as cramping, nausea/vomiting, \geq grade 2, decreased performance status, pyrexia, sepsis, neutropenia \geq grade 3, frank bleeding, and/or dehydration requiring intravenous fluid substitution.

2. **Complicated diarrhea** defined by the presence of symptoms such as cramping, nausea/vomiting, \geq grade 2, decreased performance status, pyrexia, sepsis, neutropenia \geq grade 3, frank bleeding, and/or dehydration requiring intravenous fluid substitution.

3. Loperamide should be made available prior to start of study treatment so loperamide administration can begin at the first signs of diarrhea.

4. Escalation of trametinib to previous dose level is allowed after consultation with the medical monitor and in the absence of another episode of complicated or severe diarrhea in the 4 weeks subsequent to dose reduction.

6.1.5 Trametinib Dose Modification for Liver Chemistry Changes

Trametinib Dose Modification for Liver Function Test Abnormalities	
Event	Treatment modifications and assessment/monitoring
ALT \geq 3x ULN but <5 x ULN and TB <2 x ULN, without symptoms considered related to liver injury or hypersensitivity and who can be monitored weekly for 4 weeks	
 May continue study drug. Report as SAE if CTEP-AERS reporting criteria is met. If liver chemistry stopping criteria are met any time, proceed as described below. 
MONITORING: Repeat LFT (ALT, AST, ALK, bilirubin) until they return to normal/baseline or stabilise (LFT may be every 2 weeks after 4 weeks if ALT <3x ULN and TB <2 ULN).

Criteria for discontinuing study drug: When any of the liver stopping criteria below is met, discontinue trametinib 
 1. ALT \geq3xULN and bilirubin \geq2x ULN or $>35\%$ direct bilirubin ^{1,2} 	
 Immediately discontinue study treatment. Do not restart/rechallenge unless approved by CTEP trametinib medical monitor. Report as SAE if: 1) CTEP-AERS reporting criteria are met, or 2) patients meet criteria 1-2. Perform liver event ASSESSMENT AND WORKUP (see below). Monitor the subject until liver chemistries resolve, stabilize, or return to

Trametinib Dose Modification for Liver Function Test Abnormalities	
Event	Treatment modifications and assessment/monitoring

2. ALT \geq 3xULN and INR >1.5, if INR measured² (INR threshold does not apply if subject is on anticoagulant)
 
3. ALT \geq 5x ULN
 
4. ALT \geq 3x ULN persists for \geq 4 weeks
 
5. ALT \geq 3x ULN and cannot be monitored weekly for 4 weeks
 
6. ALT \geq 3x ULN associated with symptoms³ (new or worsening) believed to be related to liver injury or hypersensitivity
	
baseline (see MONITORING below).
 
MONITORING:
 
In patients stopping for criteria 1-2 (with abnormal TB and INR, indicating potentially more significant liver toxicities):
 
 • Repeat liver chemistries (ALT, AST, ALK, bilirubin) and perform liver event follow-up assessments within 24 hours. • Monitor subjects twice weekly until LFT return to normal/baseline or stabilize. • A specialist or hepatology consultation is recommended. 
In patients stopping for criteria 2-6:
 
 • Repeat LFT and perform liver event follow up assessments within 24-72 hrs • Monitor subjects weekly until LFTs return to normal/baseline or stabilize. 
ASSESSMENT and WORKUP:
 
 • Viral hepatitis serology.⁴ • If possible, obtain blood sample for PK analysis.⁵ • Serum CPK and LDH. • Fractionate bilirubin, if total bilirubin \geq 2x ULN. • CBC with differential to assess eosinophilia. • Record clinical symptoms of liver injury, or hypersensitivity on AE CRF. • Record concomitant medications (including acetaminophen, herbal remedies, other over the counter medications). • Record alcohol use. 
Additional work up for patient stopping for criteria 1-2 (with abnormal TB and INR, indicating potentially more significant liver toxicities):
 
 • Anti-nuclear antibody, anti-smooth muscle antibody, Type 1 anti-liver kidney microsomal antibodies, and quantitative total immunoglobulin G (IgG or gamma globulins). • Serum acetaminophen adduct HPLC assay (in subjects with likely acetaminophen use in the preceding). • If there is underlying chronic hepatitis B (e.g. positive hepatitis B surface antigen): quantitative hepatitis B DNA and hepatitis delta antibody.⁶ • Liver imaging (ultrasound, MRI, CT) and /or liver biopsy.

Footnotes:

1. Serum bilirubin fractionation should be performed if testing is available. If serum bilirubin fractionation testing is unavailable, record presence of detectable urinary bilirubin on dipstick, which indicates direct bilirubin elevations and suggesting liver injury.
2. All events of ALT \geq 3xULN and bilirubin \geq 2xULN ($>35\%$ direct bilirubin) or ALT \geq 3x ULN and INR >1.5 (if INR measured) may indicate severe liver injury (possible “Hy’s Law”). INR measurement is not required, and the threshold value stated will not apply to subjects receiving anticoagulants.
3. New or worsening symptoms believed to be related to liver injury (such as fatigue, nausea, vomiting, right upper quadrant pain or tenderness, or jaundice) or believed to be related to hypersensitivity (such as fever, rash or eosinophilia)
4. Includes: Hepatitis A IgM antibody; Hepatitis B surface antigen and Hepatitis B Core Antibody (IgM); Hepatitis C RNA; Cytomegalovirus IgM antibody; Epstein-Barr viral capsid antigen IgM antibody (or if

Trametinib Dose Modification for Liver Function Test Abnormalities	
Event	Treatment modifications and assessment/monitoring
unavailable, obtain heterophile antibody or monospot testing); Hepatitis E IgM antibody 5. PK sample is desired if feasible. Record the date/time of the PK blood sample draw and the date/time of the last dose of study treatment prior to blood sample draw on the CRF. If the date or time of the last dose is unclear, provide the subject's best approximation. If the date/time of the last dose cannot be approximated OR a PK sample cannot be collected in the time period indicated above, do not obtain a PK sample. 6. If hepatitis delta antibody assay cannot be performed, it can be replaced with a PCR of hepatitis D RNA virus (where needed) (Le Gal et al. , 2005).	

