10. STUDY CALENDAR

Baseline evaluations are to be conducted within 2 weeks prior to patient registration. Tumor imaging, cardiac evaluation and ophthalmology evaluations must be done within 30 days prior to patient registration. In the event that the patient's condition is deteriorating, laboratory evaluations should be repeated within 48 hours prior to initiation of the next cycle of therapy. The window for cycle visits is +/- 7 days.

	Pre-Study	Wk 1	Wk 2	Wk 3	Wk 4	Wk 5	Wk 6	Wk 7	Wk 8	Wk 9	Wk 10	Wk 11	Wk ⁱ 12	Off Treatment
Trametinib Daily		A	A	A	A	A	A	A	A	A	A	A	A	
Informed consent	X													
Archival tumor tissue sent for TAZ-CAMTA1 FISH	X													
Demographics	X													
Medical history	X													
Concurrent meds	X	X-----									X			
Physical exam	X	X		X		X				X				X
Vital signs	X	X				X				X				X
Height	X													
Weight	X	X				X				X				X
Performance status	X	X				X				X				X
CBC w/diff, plts	X	X		X		X				X				X
Serum chemistry ^a	X	X		X		X				X				X
ESR, CRP ^b	X					X								
Plasma collection for CTGF ^b	X					X								
EKG	X													
Echocardiogram or MUGA ^c	X													Every 12 weeks (+/- 14 days) (use same methodology for baseline and follow up).
Ophthalmology exam ^d	X													
Adverse event evaluation		X-----									X			X
Tumor measurement ^e	X													X
Radiologic evaluation ^f	X													X
Pregnancy test ^g	X													
Optional fresh biopsy of tumor	X				X									
NIH PROMIS Questionnaire ^h	X				X									

A: Trametinib: Dose as assigned; to be taken daily

a: Comprehensive metabolic panel. The panel should include albumin, alkaline phosphatase, total bilirubin, bicarbonate, BUN, calcium, chloride, creatinine, glucose, potassium, total protein, SGOT [AST], SGPT [ALT], sodium.

b: Biomarker assessment: ESR-westergren method preferred and CRP, to be performed by local lab prior to therapy, after 4 weeks and 6 months of treatment (for patients with stable for better disease), at time of objective response and at progression. Plasma for

- determination of CTGF level to be obtained at the same time points and sent to central lab for analysis.
- c: The same modality (ECHO or MUGA) should be used at baseline and at follow-up
- d: Ophthalmology exams should be obtained at baseline, and if clinically indicated, during study. Ophthalmology exam should include Ocular Coherence Tomography, fundoscopy, tonometry, visual field examination, and corrected visual acuity assessments.

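### Liver stopping criterion 2 sits under two conflicting follow-up schedules; the second heading should read criteria 3-6

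*Combined protocol and SAP*

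**What the plan says.** Section 6.1.5 of the combined protocol and SAP lists six criteria for stopping trametinib on liver chemistry. Criterion 1 combines ALT at or above 3 times ULN with raised bilirubin. Criterion 2 combines the same ALT level with INR above 1.5, if INR was measured. Criteria 3 to 6 rest on ALT alone (at least 5 times ULN), or on ALT at or above 3 times ULN that persists, cannot be monitored weekly, or comes with symptoms.

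The monitoring instructions then fall under two headings:

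- "In patients stopping for criteria 1-2 (with abnormal TB and INR, indicating potentially more significant liver toxicities": repeat chemistries and follow-up assessments within 24 hours, twice-weekly checks, and a specialist or hepatology consultation recommended.
- "In patients stopping for criteria 2-6": repeat tests within 24 to 72 hours, then weekly checks.

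Elsewhere in the section, SAE reporting is triggered if "patients meet criteria 1-2", the extra tests are headed "Additional work up for patient stopping for criteria 1-2 (with abnormal TB and INR", and footnote 2 says that the patterns in criteria 1 and 2 both "may indicate severe liver injury".

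**The concern.** Criterion 2 appears under both headings, with different instructions and no statement of precedence. The conflict falls on a pattern that footnote 2 names as possible Hy's Law, where early retesting and close follow-up matter most. A site working from the second heading alone could put such a patient on the lighter schedule and still claim to have followed the protocol. Sites and auditors could also disagree on whether weekly follow-up of a criterion 2 patient is a deviation.

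**Working it through.** No sample size, power or error rate is involved. The check has three parts: compare the criterion numbers under the two headings, see how the rest of the section groups criterion 2, and size the difference.

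**1. Coverage as written.** The first heading covers {1, 2} and the second {2, 3, 4, 5, 6}. That is 2 + 5 = 7 assignments for 6 criteria, and the shared element is criterion 2 only.

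**2. The two instructions for criterion 2.**

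| Item | First heading (1-2) | Second heading (2-6) |
|---|---|---|
| First retest | within 24 h | within 24-72 h |
| Later checks | twice weekly | weekly |
| Specialist or hepatology consultation | recommended | not mentioned |

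The largest gap in the first-retest deadline is 72 h - 24 h = 48 h. The later checks are half as frequent under the second heading.

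**3. Which heading is wrong.** Four places in Section 6.1.5 put criterion 2 with criterion 1: the SAE rule, the first monitoring heading, the additional work-up heading and footnote 2. The first monitoring heading also refers to abnormal INR, and INR enters the list only through criterion 2. Limiting that heading to criterion 1 would remove the overlap but contradict its own wording. The repair that fits the section is to start the second heading at 3.

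**4. Coverage after the change.** {1, 2} and {3, 4, 5, 6} give 2 + 4 = 6 assignments for 6 criteria, with no number repeated and none missing.

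**5. How many patients.** The documents give no rate for criterion 2. Three facts suggest a very small number:

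- Footnote 2 of Section 6.1.5 states: "INR measurement is not required, and the threshold value stated will not apply to subjects receiving anticoagulants".
- The chemistry panel in Section 10, footnote a ("The panel should include albumin, alkaline phosphatase, total bilirubin" and further items) does not list INR.
- Section 13.2 plans 27 fusion-positive patients plus replacements.

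Section 2.2.1.3 reports liver test abnormalities in 8% to 34% of patients across five trials at 2 mg monotherapy. Those figures cover liver tests generally and cannot be turned into a rate for criterion 2.

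**The case against.** The strongest reply is that this is an obvious slip with little consequence. The intended grouping can be read from the same table. The two schedules are also largely compatible: twice-weekly checks satisfy a weekly requirement, and a site reading both headings would follow the stricter one. Trametinib is still stopped at once, rechallenge still needs medical monitor approval, and SAE reporting and the additional work-up still apply. A clinician who has chosen to order an INR probably suspects serious injury already, although that is inference and not in the documents. Stage I had already enrolled when this version was written (Section 13.1), so the edit helps only patients still on or entering treatment.

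These points limit the size of the problem, but they do not make the heading right. A safety instruction should not depend on sites noticing a numbering error and resolving it for themselves.

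A further point stands in full. The six criteria are not mutually exclusive. A patient with ALT at least 5 times ULN and INR above 1.5 meets criteria 2 and 3, and would fall under both headings even after renumbering. The correction removes the overlap in the numbering, not every case in which one patient meets criteria from both groups.

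**Conclusion.** The concern holds. Criterion 2 is assigned to two different follow-up schedules, and the second heading is the one in error. At most, the first retest is 48 hours later, checks are weekly instead of twice weekly, and the recommended consultation is omitted. That harm requires a site to follow the second heading alone. Few if any patients are likely to be affected, given that INR is optional and the trial is small, but the documents do not allow a count. The primary endpoint, the sample size and the analysis are untouched. That the intended range is 3-6 is an inference, supported by the four places in the section that pair criteria 1 and 2. The error is worth correcting because it concerns a safety rule for possible severe liver injury.

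**What to change.** In the second monitoring heading of the Section 6.1.5 table, replace the range 2-6 with 3-6. This is one digit in one heading. It reduces no patient's follow-up, leaves the schedule for criteria 3 to 6 as it is, and needs no change to data collection, sample size or analysis.

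An optional added sentence, saying that a patient who meets criteria from both groups follows the stricter schedule, would settle the remaining cases.

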6.1.6 Trametinib Dose Modification for Pneumonitis

Pneumonitis has been observed in patients receiving trametinib. To reduce the risk of pneumonitis, patients will be monitored closely for symptoms and evaluated with imaging and functional tests. Dose modification and supportive care guidelines for pneumonitis are described in the tables below.

Pneumonitis Guidelines for Trametinib Monotherapy		
CTCAE Grade	Adverse Event Management	Action and Dose Modification
Grade 1	
 • CT scan (high-resolution with lung windows) recommended. • Work-up for infection • Monitoring of oxygenation via pulse-oximetry recommended • Consultation with pulmonologist recommended 	
 • Continue trametinib at current dose
Grade 2	
 • CT scan (high-resolution with lung windows) recommended. • Work-up for infection • Consult pulmonologist • Pulmonary function tests – if < normal, repeat every 8 weeks until \geq normal • Bronchoscopy with biopsy and/or BAL recommended • Symptomatic therapy including corticosteroids if clinically indicated 	
 • Permanently discontinue trametinib if pneumonitis is related to treatment.
Grade 3	
 • Same as grade 2 	
 • Permanently discontinue trametinib
Grade 4	
 • Same as grade 2 	
 • Permanently discontinue trametinib

6.1.7 Trametinib Dose Modification for Reduced Left Ventricular Ejection Fraction

Decreases of the left ventricular ejection fraction (LVEF) have been observed in patients receiving trametinib. Therefore, ECHO/MUGAs must be performed in regular intervals outlined in the Study Calendar. The same procedure (either ECHO or MUGA, although ECHO is preferred) should be performed at baseline and at follow-up visit(s).

Trametinib Dose Modification Guidelines and Stopping Criteria for LVEF Decrease		
Clinic	LVEF-drop (%) or CTCAE grade	Action and Dose Modification
Asymptomatic	Absolute decrease of >10% in LVEF compared to baseline and ejection fraction below the institution's LLN.	
 Interrupt trametinib and repeat ECHO/MUGA within 2 weeks.^a If the LVEF recovers within 4 weeks (defined as LVEF \geqLLN and absolute decrease \leq10% compared to baseline): 
 Consult with the CTEP trametinib medical monitor and request approval for restart. Restart treatment with trametinib at reduced dose by one dose level.^b Repeat ECHO/MUGA 2, 4, 8, and 12 weeks after re-start; continue in intervals of 12 weeks thereafter. If LVEF does not recover within 4 weeks: 
 Consult with cardiologist. Permanently discontinue trametinib. Report as SAE Repeat ECHO/MUGA after 2, 4, 8, 12, and 16 weeks or until resolution. Consult with the CTEP trametinib medical monitor.^c
Symptomatic^b	
 Grade 3: resting LVEF 39-20% or $>20\%$ absolute reduction from baseline Grade 4: Resting LVEF $\leq 20\%$. 	
 Permanently discontinue trametinib. Report as SAE. Consult with cardiologist. Repeat ECHO/MUGA after 2, 4, 8, 12, and 16 weeks or until resolution.

^a If ECHO/MUGA does not show LVEF recovery after 2 weeks, repeat ECHO/MUGA 2 weeks later.

^b Escalation of trametinib to previous dose level can be considered if LVEF remains stable for 4 weeks after restarting of trametinib. Approval from the CTEP trametinib medical monitor is required.

^c Symptoms may include: dyspnea, orthopnea, and other signs and symptoms of pulmonary congestion and edema.

6.1.8 Trametinib Dose Modification for QTc Prolongation

Trametinib Withholding and Stopping Criteria for QTc Prolongation	
QTc Prolongation ^a	Action and Dose Modification

• QTcB \geq501 msec, or• Uncorrected QT $>$600 msec, or• QTcB $>$530 msec for subjects with bundle branch block	
• Interrupt study treatment until QTcB prolongation resolves to grade 1 or baseline.• Test serum potassium, calcium, phosphorus, and magnesium. If abnormal, correct per routine clinical practice to within normal limits.• Review concomitant medication usage for a prolonged QTc.• Restart at current dose level.^b• If the event does not resolve or recurs after restarting, permanently discontinue study treatment.

Abbreviations: msec = milliseconds; QTcB = QT interval on electrocardiogram corrected using Bazett's formula

^a Based on average QTc value of triplicate ECGs. For example, if an ECG demonstrates a prolonged QT interval, obtain two or more ECGs over a brief period, and then use the averaged QTc values of the three ECGs to determine if study treatments should be interrupted or discontinued.

^b if the QTc prolongation resolves to grade 1 or baseline, the subject may resume study treatment if the investigator and the CTEP trametinib medical monitor agree that the subject will benefit from further treatment.

6.1.9 Trametinib Dose Modification for Hypertension

Increases in blood pressure (BP) have been observed in patients receiving trametinib. Recommendations for BP monitoring and management are provided below.

Monitoring: All BP assessments should be performed under the following optimal conditions:

The subject has been seated with back support, ensuring that legs are uncrossed and flat on the floor.

The subject is relaxed comfortably for at least 5 minutes.

Restrictive clothing has been removed from the cuff area, and the right cuff size has been selected.

The subject's arm is supported so that the middle of the cuff is at heart level.

The subject remains quiet during the measurement.

In subjects with an initial BP reading within the hypertensive range, a second reading should be taken at least 1 minute later, with the two readings averaged to obtain a final BP measurement. The averaged value should be recorded in the eCRF.

Persistent hypertension is defined as an increase of systolic blood pressure (SBP) $>$ 140 mmHg and/or diastolic blood pressure (DBP) $>$ 90 mmHg in three consecutive visits with blood pressure assessments from two readings as described above. Visits to monitor increased blood pressure can be scheduled independently from the per-protocol visits outlined in the study calendar. Ideally, subsequent blood pressure assessments should be performed within 1 week.

Management and Trametinib Dose Modification for Hypertension		
Event	Management Guideline	Dose Modification
Definitions used in the table:		

 - Persistent hypertension: Hypertension detected in two separate readings during up to three subsequent visits. - Well-controlled hypertension: Blood pressure of SBP \leq140 mmHg and DBP \leq90 mmHg in two separate readings during up to three subsequent visits. - Symptomatic hypertension: Hypertension associated with symptoms (e.g., headache, light-headedness, vertigo, tinnitus, episodes of fainting or other symptoms indicative of hypertension) that resolve after the blood pressure is controlled within the normal range. - Asymptomatic hypertension: SBP $>$140 mmHg and/or DBP $>$90 mmHg in the absence of the above symptoms. 		
(Scenario A) 
 - Asymptomatic and persistent SBP of \geq140 and $<$160 mmHg, or DBP \geq90 and $<$100 mmHg, or Clinically significant increase in DBP of 20 mmHg (but still below 100 mmHg). 	
 • Adjust current or initiate new antihypertensive medication(s). • Titrate antihypertensive medication(s) during the next 2 weeks to achieve well-controlled BP. If BP is not well-controlled within 2 weeks, consider referral to a specialist and go to scenario (B). 	Continue trametinib at the current dose.
(Scenario B) 
 - Asymptomatic SBP \geq160 mmHg, or DBP \geq100 mmHg, or Failure to achieve well-controlled BP within 2 weeks in Scenario A. 	
 • Adjust current or initiate new antihypertensive medication(s). • Titrate antihypertensive medication(s) during the next 2 weeks to achieve well-controlled BP. 	
 • Interrupt trametinib if clinically indicated. • Once BP is well-controlled, restart trametinib reduced by one dose level.^a
(Scenario C) 
 - Symptomatic hypertension or Persistent SBP \geq160 mmHg, or DBP \geq100 mmHg, despite antihypertensive medication and dose reduction of trametinib 	
 • Adjust current or initiate new antihypertensive medication(s). • Titrate antihypertensive medication(s) during the next 2 weeks to achieve well-controlled BP. • Referral to a specialist for further evaluation and follow-up is recommended. 	
 • Interrupt trametinib. • Once BP is well-controlled, restart trametinib reduced by one dose level.^a
(Scenario D) Refractory hypertension unresponsive to above interventions or hypertensive crisis.	Continue follow-up per protocol.	Permanently discontinue trametinib.
a. Escalation of trametinib to previous dose level can be considered if BPs remain well controlled for 4 weeks after restarting of trametinib. Approval from Medical Monitor is required.		

